2.3 RISK/BENEFIT ASSESSMENT

2.3.1 KNOWN POTENTIAL RISKS

There are several potential risks associated with the EAW and the testing procedures.

- 1) EAW training has the potential risks of hypotension, falls resulting in bone fracture, muscle soreness, joint damage, or other musculoskeletal injury, and/or autonomic dysreflexia (AD).
- 2) Persons using the Ekso may also be at risk for bruising, skin abrasion, pressure sores, soft tissue injury, or adverse tissue reaction from direct contact of the body with the device. Notable contact points exist between the sacrum and back pack, hip pads and greater trochanters, shin pads and shins, and with the straps for the thighs and legs.
- 3) Other possible risks to exoskeleton use include discomfort, triggered spasms, reflex bowel or bladder activity, diastolic hypertension and changes in blood pressure and heart rate, or autonomic instability during use of the device.
- 4) The person operating the controller could initiate a use error by incorrectly inputting individual participant specifications which could affect the participant's ability to move correctly with the device thus increasing risk to the participant.
- 5) Lastly, the device itself could malfunction due to premature battery failure, interference with other electrical equipment or devices, electrical shock, or unanticipated operation (stoppage or unintended movement).
- 6) Psychological risks could include anxiety (e.g., when you begin walking training), altered mood when you complete the questionnaires, and depression (e.g., when you end the study).
- 7) Risk of loss of private information; this risk always exists, but there are procedures in place to minimize the risk.

2.3.2 KNOWN POTENTIAL BENEFITS

There is no expected benefit to subjects. However, possible benefits may be improving subjects' activities of daily living or reducing their pain or systemic inflammation from early intervention of walking training using EAW, although it is not guaranteed. These benefits may not continue after subjects discharge from the hospital and stop the walking training.

3 OBJECTIVES AND ENDPOINTS

OBJECTIVES	ENDPOINTS
Primary	
To determine the effects of AIR with EAW compared with AIR without EAW (same total therapy time) on the changes from admission to discharge in the International Standards for Neurological Classification of Spinal Cord Injury (ISNCSCI) upper and lower extremity motor scores, Functional Independence Measure (FIM) scores, and Spinal Cord Independence Measure (SCIM) scores as classified by clinicians.	ISNCSCI examination results FIM scores SCIM scores
Secondary	
To determine the effects of AIR with EAW compared to AIR without EAW on reducing pain using the International Spinal Cord Injury Basic Pain Data Set 2.0 (ISCIBPDS 2.0) measures where type of pain is classified with the Spinal Cord Injury Pain Instrument (SCIPI).	Intensity of pain
Tertiary/Exploratory	
To determine the effects of AIR with EAW compared with AIR without EAW on reducing a specific systemic inflammatory mediator (C reactive protein, CRP).	CRP results

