Study Population: Individuals with SCI who stay in the SCI acute inpatient rehabilitation

Phase: NA

Description of Sites/Facilities Enrolling Participants: Icahn School of Medicine at Mount Sinai

Description of Study Intervention: In the intervention group, participants will receive locomotor training provided with an Ekso™ powered exoskeleton. The EAW training will be incorporated into the designated therapy times (3 hours of physical therapy (PT) and/or occupational therapy (OT)).

Study Duration: 3 years

Participant Duration: Twenty to thirty minute per session, one session a day, equal or more than 3 sessions/days per week, from enrollment in the study to discharge from the acute inpatient rehabilitation. Different participants have different duration of participation based on their length of inpatient stay.

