2.2 BACKGROUND

Paralysis from traumatic SCI results in an abrupt reduction in the level of daily physical activity. Depending on the neurological level and completeness of SCI, those with more severe SCI may lose neuromuscular control of the upper extremities, trunk, and/or lower extremities which can result in a loss of the ability to sit, stand and walk and to perform activities of daily living (ADLs). For people with SCI, the ability to walk consistently rank at the top of their priority list for recovery [1, 2]. Most feel that their quality of life is lower than it could be without SCI due to difficulties in independently performing daily activities, finding a job or vocation, and challenges in participating in all that a community may offer [3]. Reductions in physical activity and other physical changes also promote pain in individuals with SCI, including the two main subtypes of neuropathic and nociceptive musculoskeletal pain [4]. Approximately 80% of people with SCI experience ongoing pain [5], and about 20% of people with SCI indicate that this pain interferes with work and daily activities [6]. Furthermore, immobilization and paralysis after SCI often leads to a sedentary life style resulting in loss of muscle mass and gain of adiposity [7]. This change in ratio of muscle to fat mass predisposes to insulin resistance and the development of type II diabetes mellitus as well as to obesity [7-10]. A compromised immune system has also been reported to occur after SCI with evidence of increased markers of systemic inflammation, including elevated CRP [11-15]. Changes in cholesterol and triglyceride levels as well as immunosuppression, such as reduced natural killer, T-cell, and lymphocyte functions, have also been reported [11-16]. The inflammatory response may also play an important role in the modulation of pain after SCI [17, 18]. Clinical data shows that elevated inflammatory mediators are present in persons with acute or chronic SCI, including factors that mediate pain in preclinical models [14, 19-21]. Reductions of functional activity and increased pain and inflammatory response all worsen each other, negatively impacting an individuals' quality of life.

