Powered exoskeletons are a technology that can offer overground locomotion for people with SCI who would ordinarily be unable to walk and have been suggested as a way to promote increased function and quality of life [39]. In studies pioneered by [name] (co-mentor), exoskeletons have been studied in the chronic (>6 months post) SCI population for about seven years with preliminary reports showing benefits in mobility, health and quality of life (QOL) outcomes [40, 41]. While walking in an exoskeleton, people with SCI stand upright with full weight bearing through the feet [41] and walk while activating trunk and lower limb muscles. This activation may facilitate improvements in neuroconnectivity [39]. EAW has several benefits over BWSTT. It provides ground gait training experience that offers the potential benefits of standing and gait training with just one trainer and requires less of a constant equipment space allotment in an inpatient rehabilitation setting. EAW also possesses the unique potential for use after inpatient discharge to continue training and allow functional use in home, work, and community settings.

Previous studies show that EAW can elicit moderate-intensity activity for people with SCI, and participants can learn to walk without hands-on physical assistance by another person [40, 42-44]. Subjective reports from inpatients who were given the opportunity to use an exoskeleton during AIR in Mount Sinai Hospital had comments such as: "it was really great to have the legs moving again", "walking helped with regaining trunk support" and resulted in "good sensations in the legs and feet".

Despite the potential functional and health benefits of using EAW training in persons in SCI AIR, there are few studies published that have used, or are using an EAW intervention in early inpatient rehabilitation for patients with acute/sub-acute SCI. As such, there is a critical gap in knowledge that limits the use of EAW across the clinical care spectrum in SCI: we don't know if the EAW can be

effectively incorporated in clinical practice and if adding EAW into AIR program is better than traditional AIR without EAW. We expect this prospective randomized control trial (RCT) to determine if EAW training during AIR is a feasible, safe and efficacious approach to facilitate functional independence and to reduce post-SCI pain, as well as inflammation.

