4 STUDY DESIGN

4.1 OVERALL DESIGN

A two-group, single-blinded (raters are not part of intervention) and randomized clinical trial (RCT) with stratification for traumatic or non-traumatic injury will be performed. The stratification will help to ensure balanced groups prior to randomization.

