5 STUDY POPULATION

5.1 INCLUSION CRITERIA

1. Age 18 years or greater
2. Height between 5'2" and 6'2" (1.6 meters to 1.9 meters)
3. Weight less than 220 pounds (100 kilograms)
4. Near Normal range of motion (ROM), as follows: 1) Hip: more than 5 degrees of extension and 110 degrees of flexion; 2) Knee: Full extension to 110 degrees of flexion; 3) Ankle: at least 0 degree of dorsiflexion to 25 degrees of plantarflexion
5. Are eligible for locomotor training as part of inpatient rehabilitation
6. Independent with static sitting balance
7. Sufficient function upper extremity strength to manage walking aid (front-wheeled walker, platform walker, or crutches)
8. Able to follow directions

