8 STUDY ASSESSMENTS AND PROCEDURES

8.1 EFFICACY ASSESSMENTS

Demographic data:

1. Age: age of patient in years
2. Sex: male (M) or female (F)
3. Race: race of patient
4. Diagnosis: primary diagnosis of the patient from medical chart (include level of injury from the International Standard for Neurological Classification of Spinal Cord Injury (ISNCSCI) examination and the completeness of injury from American Spinal Injury Association Impairment Scale (AIS)) at admission and discharge.
5. Date (or year) of injury: the date of getting the diagnosis
6. Admission date: the date that the patient starts acute inpatient rehabilitation
7. Discharge date: the date that the patient discharged

Pain scale: 1) International Spinal Cord Injury Basic Pain Data Set (ISCIBPDS) to identify pain locations, average intensity (over the past three days), and influence on daily activities. 2) Spinal Cord Injury Pain Instrument (SCIPI) to classify patients' neuropathic or nociceptive pain. ISCIBPDS and SCIPI will be performed on the enrollment and discharge dates. 3) Participants' current level of pain before and after walking training will be recorded in the walking session data form.

Walking session results include session date, total up time, total walk time, and total steps. If subjects can walk independently 10-meter walking test and Walking Index for Spinal Cord Injury II (WISCI II) will be tested. In the 10 MWT, the participant will be asked to walk 10 meters (without the exoskeleton) at their fastest, comfortable pace. The time to cover this distance will be timed with a stopwatch. The 20-item WISCI-II provides a rank-order rating of the ability of a person with SCI to walk 10 meters in relation to the severity of impairment. Ratings consider the amount of assistance and the types of assistive devices (e.g., leg braces) required to walk. Both the 10 MWT and WISCI II will be evaluated after enrollment (within 1-2 days) and before discharge from AIR (± 2 days).

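### The upper-extremity motor score is part of the primary endpoint but is compared without regard to injury level, so participants with no arm deficit dilute the comparison

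*Combined protocol and SAP*

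**What the plan says.** Sections 1.1 and 3 list as primary the admission-to-discharge change in "upper and lower extremity motor scores, Functional Independence Measure (FIM) scores" and SCIM scores. The endpoint column in Section 3 refers only to the ISNCSCI examination, so it is not stated whether the arm and leg scores are tested separately or as a total.

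The population in Section 1.1 is "Individuals with SCI who stay in the SCI acute inpatient rehabilitation". Neither Section 5.1 nor Section 5.2 restricts neurological level. The one criterion on arm function is "Sufficient function upper extremity strength to manage walking aid (front-wheeled walker, platform walker, or crutches", with no motor-score cut-off.

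Section 2.2 links arm deficit to level: "Depending on the neurological level and completeness of SCI, those with more severe SCI may lose neuromuscular control of the upper extremities". It describes people using the exoskeleton as able to "walk while activating trunk and lower limb muscles".

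Section 4.1 specifies a randomised trial "with stratification for traumatic or non-traumatic injury will be performed"; injury level is not a stratification factor. Section 8.1 does collect level at admission and discharge ("include level of injury from the International Standard for Neurological Classification of Spinal Cord Injury (ISNCSCI) examination"). Sections 9.1 and 9.2.1 apply one unadjusted t-test, or a Mann-Whitney test if the data are not normal, to the change in each outcome. Level is not used.

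**The concern.** If arm deficit depends on neurological level and entry is open to all levels, some participants will begin with arms that are intact or nearly so. The requirement to manage a walking aid selects further towards good arm function. These participants can show little or no gain in arm score in either group. Pooling them with participants who can gain shrinks the mean difference between groups. It also widens the spread, because people who improve are mixed with people who stay at their starting score.

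At stake is the reading of one component of the primary endpoint. A null arm-score result could reflect who was enrolled rather than whether the intervention helps arm recovery in people who have something to recover.

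**Working it through.** **Inputs from the documents.** 20 intervention and 10 control completers (Sections 6.1.1 and 6.2); d = 1.07, from FIM; two-sided alpha 0.05; t-test on change scores (Section 9.1).

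**Inputs assumed.** The documents give no cervical share, no baseline arm scores and no expected arm-score effect. I take:
- a share p of participants with a cervical level, tried at 30%, 50%, 70% and 85%;
- a treatment effect of 1.07 SD among them, borrowed from FIM;
- a control mean change m of 0.5 to 1.0 SD among them;
- zero change in everyone else.

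**The plan's own figure.** Noncentral-t power uses λ = d·√(n₁n₂/(n₁+n₂)) on n₁+n₂−2 degrees of freedom.
- 15 v 15: λ = 1.07·√7.5 = 2.93, power 80.7%. This matches the stated 80%.
- 20 v 10: λ = 1.07·√6.667 = 2.76, power 76.0%.

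The gap at 2:1 is a separate matter. Here 76% serves as the reference value if every participant could change.

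**How dilution acts.** With a share p able to change, the mean difference becomes 1.07p. A group whose changing members have mean μ and SD 1 has variance p(1+μ²) − (pμ)². For p = 0.5 and m = 1.0:
- control variance: 0.5·2 − 0.25 = 0.75;
- intervention variance (μ = 2.07): 0.5·5.285 − 1.071 = 1.571;
- pooled SD, weighted 2:1: √((2·1.571 + 0.75)/3) = 1.139;
- diluted effect: 0.535/1.139 = 0.47 SD, down from 1.07.

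**Power.** The mixture is not normal and the larger group has the larger variance, so power was simulated. The number of cervical participants in each group varied by chance.

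| Cervical share | t-test, all 30 | t-test, cervical only |
|---|---|---|
| 30% | 6–8% | about 23% |
| 50% | 17–24% | about 42% |
| 70% | 34–44% | about 58% |
| 85% | 53–60% | about 68% |

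Repeat runs agree to within about one percentage point. The ranges in the middle column run from m = 1.0 (lower power) to m = 0.5 (higher). The cervical-only column does not depend on m. As a check on it, a fixed 10 v 5 split gives λ = 1.07·√(50/15) = 1.95 and 44%; averaging over chance splits brings this to about 42%.

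**Sensitivity.** With m = 1.75 SD, power in all 30 falls further, to about 11% at a 50% share and 24% at 70%. The Mann-Whitney fallback does not recover the loss: with m = 0.5–1.0 it gives 14–21% at 50% and 31–40% at 70%.

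**Sparse subsets.** At a 30% share:
- fewer than two cervical controls: 0.7¹⁰ + 10·0.3·0.7⁹ = 0.149;
- fewer than two in the intervention group: 0.7²⁰ + 20·0.3·0.7¹⁹ = 0.008;
- either: 1 − 0.851·0.992 = 0.156.

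So in about 15–16% of such trials the cervical-only subset would be too thin to compare.

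**The case against.** The strongest reply is that the level mix is unknown. A reader might infer that the arm-score data would be mostly zeros, or that a null result is nearly certain. The documents support neither. Cervical injury is not excluded, a platform walker is an accepted aid, and strength sufficient to use an aid is not a maximum arm score. At a 70% cervical share the all-participant test still has 34–44% power. Only at the low end of the range is a null close to assured. Exactly zero change is also an idealisation: the documents do not describe how the instrument is scored, and real measurements carry some noise. Small noise in the unaffected participants does not alter the ranking of the two tests.

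A reader might also infer that adding arm and leg scores together must harm the motor comparison. That holds only if the arm effect is near zero. With the 1.07 SD used here and an independent leg score with the same effect and SD, the leg score alone has 76% power. The sum has 72–79% at a 30% cervical share, 78–84% at 50% and 85–90% at 70%. Summing is not shown to be harmful; the documented gap is that the plan does not say which is done.

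It is fair, too, that Section 9.1 names FIM as the primary aim and sizes the trial on FIM alone, and that nothing says a null arm score defeats the primary hypothesis. That all 30 would enter the arm-score test is itself inferred from the absence of any restriction, since the inclusion sentence in Section 9.2.1 mentions only participants with EAW sessions. Finally, a subset test at 23–68% power is still modest.

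What remains is that restricting by admission level gave more power at every share tried, so the recommendation does not depend on knowing the mix.

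**Conclusion.** The point holds as a loss of power and of interpretability on one co-listed primary measure. It is not bias, and the FIM sample size is untouched. Analysing the arm score without regard to level costs roughly 8 to 25 percentage points of power over cervical shares of 30% to 85%: 60% v 68% at the narrowest, 17% v 42% at the widest.

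These sizes rest on an effect borrowed from FIM, an assumed control change, and little or no change in participants without arm deficit. The direction is firmer than the sizes. Whether the arm score should stay primary or become supportive is partly a matter of preference, and the documents do not settle it. This is a cheap improvement, not a flaw that threatens the trial.

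**What to change.** In Sections 1.1, 3 and 9.2.1, state that the upper- and lower-extremity motor scores are analysed separately: the lower-extremity score in all participants, and the upper-extremity score in participants whose admission neurological level is cervical. Give the expected level mix if it is known, and confirm against the instrument's scoring rules that a cervical level is the right cut.

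Add a rule for a sparse subset. If either group has fewer than two cervical participants, report the arm score descriptively. Alternatively, analyse all participants with adjustment for cervical level; under the same assumptions this gives nearly the same power as the restricted test. Its estimate is then an average that includes participants with little room to change, and should be described as such.

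The cost is wording only. Level is already collected, no participants are added, and because the subset is defined by an admission value the comparison within it remains randomised. The downside is an arm-score estimate based on fewer people, with balance within the subset left to chance because level is not a stratification factor.

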4 STUDY DESIGN

4.1 OVERALL DESIGN

A two-group, single-blinded (raters are not part of intervention) and randomized clinical trial (RCT) with stratification for traumatic or non-traumatic injury will be performed. The stratification will help to ensure balanced groups prior to randomization.

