9.2 STATISTICAL ANALYSES

9.2.1 GENERAL APPROACH

All statistical tests will be 2-sided. The outcome measures will be tested at a 0.05 level of significance. SPSS will be used to conduct the statistical analyses. All participants who have EAW sessions will be included (regardless of the number of sessions they complete before discharge, but the number and reason of missing EAW sessions will be recorded). To test the three main hypotheses of the proposed study, the change score of each outcome between baseline and discharge will be calculated. The change score will be compared between the intervention and control groups using independent t-test analyses (if the outcomes are not normally distributed, Mann-Whitney tests will be used).

In addition to the primary analysis, several secondary analyses will be performed. 1) Each of the outcomes will be compared between pre- and post-EAW training using a paired t-test analysis (if the outcomes are not normally distributed, Wilcoxon signed-rank test will be used). 2) Analyses will be performed to determine the relationships between the change of outcome measures and EAW training time (including sessions, up time, walking time, or total number of steps per session and across all sessions) using correlation coefficients, regression analyses (stepwise and logistic), analyses of covariance, and nonparametric analyses as appropriate. 3) An additional exploratory post

hoc analyses will be to determine the relationship of participant's baseline characteristics with successful use of the exoskeleton. This post hoc analysis would serve as pilot data to begin to determine who is a good candidate for EAW training during AIR for a future study.

References:

1. Simpson, L.A., et al., *The health and life priorities of individuals with spinal cord injury: a systematic review*. J Neurotrauma, 2012. **29**(8): p. 1548-55.
2. Ditunno, P.L., et al., *Who wants to walk? Preferences for recovery after SCI: a longitudinal and cross-sectional study*. Spinal Cord, 2008. **46**(7): p. 500-6.
3. Tate, D.G., C.Z. Kalpakjian, and M.B. Forchheimer, *Quality of life issues in individuals with spinal cord injury*. Arch Phys Med Rehabil, 2002. **83**(12 Suppl 2): p. S18-25.
4. [name], T.N. and K.T. Ragnarsson, *Pain after spinal cord injury*. Phys Med Rehabil Clin N Am, 2000. **11**(1): p. 157-68.

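### Injury completeness is handled neither in the allocation nor in the main between-group analysis, which leaves a 20:10 trial exposed to chance imbalance and lost precision

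*Combined protocol and SAP*

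**What the plan says.** **Allocation.** Section 4.1 states that "stratification for traumatic or non-traumatic injury will be performed. The stratification will help to ensure balanced groups prior to randomization". Section 6.2 adds only the split of 20 to exoskeletal-assisted walking (EAW) and 10 to control. It names no other factor and no minimisation.

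**Severity.** The background in Section 2.2 says: "Depending on the neurological level and completeness of SCI, those with more severe SCI may lose neuromuscular control". The same sentence goes on to the loss of sitting, standing, walking and daily activities. It gives cause of injury no such role. Section 8.1 lists among the baseline data "the completeness of injury from American Spinal Injury Association Impairment Scale (AIS)) at admission and discharge". Sections 5.1 and 5.2 set no limit on AIS grade or neurological level.

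**Analysis.** Section 9.2.1, repeating Section 9.1, says: "The change score will be compared between the intervention and control groups using independent t-test analyses". A Mann-Whitney test replaces the t-test if the data are not normal. Analysis of covariance appears only among the secondary analyses that relate outcome change to EAW training time.

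**The concern.** The primary outcomes are motor scores, FIM and SCIM, the same domains that Section 2.2 ties to level and completeness. The protocol invokes stratification in order to balance the groups, yet the factor it chooses is not the one its own background connects with function. The analysis does not make up for this, because the between-group test carries no baseline variable, not even the stratification factor.

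With 10 controls, one person is 10% of that arm, so a noticeable difference in injury mix can arise by chance. If recovery on FIM differs by completeness, that difference moves the estimate, and the planned analysis cannot separate it from the effect of EAW in the trial as run. An adjusted analysis could largely do so, from data already collected.

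**Working it through.** **The plan's own figure.** Section 9.1 gives FIM change of 35 ± 12 v 22 ± 13 (difference 13), effect size 1.07, two-sided 0.05, 30 completers and 80% power. The normal approximation at 20:10 gives 78.9%. The exact t-test gives 80.7% at 15:15 and 76.0% at 20:10. Enrolment is 30/(1 − 0.25) = 40, as stated. The present point does not rest on the power figure.

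**Standard error.** Pooled variance = (19 × 12² + 9 × 13²)/28 = 4257/28 = 152.0, so SD = 12.33. SE = 12.33 × √(1/20 + 1/10) = 4.78 FIM points.

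**Chance imbalance.** Let K of the 30 completers have complete injuries, and let X be the number of these in the control arm. Without stratification on completeness, X is hypergeometric (30, K, 10). The difference in share is D = X/10 − (K − X)/20 = 0.15X − K/20. The documents do not give K; I assume 20% to 50%, that is 6 to 15.

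| K (share) | P(absolute D ≥ 30 points) | SD of D |
|---|---|---|
| 6 (20%) | 14.1% | 15.8 points |
| 7 (23%) | 6.4% | 16.7 |
| 8 (27%) | 7.8% | 17.4 |
| 9 (30%) | 20.4% | 18.1 |
| 10 (33%) | 10.1% | 18.6 |
| 12 (40%) | 23.5% | 19.3 |
| 15 (50%) | 24.5% | 19.7 |

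K = 11, 13 and 14 give 10.8%, 11.9% and 12.2%. The probability jumps because D moves in steps of 15 points. The SD is the steadier summary, at 16 to 20 points. At K = 15 the event is X ≤ 3 or X ≥ 7, at 12.3% in each direction.

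Two limits apply. The calculation assumes that cause is unrelated to completeness; if they are related, stratifying by cause already gives partial protection. It also refers to the 30 completers. If all 40 enrolled were randomised and analysed (about 27:13), the chance of a 30-point difference would be 0.8% to 8.6% at shares of 20% to 50%, with an SD of 14 to 17 points.

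**Shift in the estimate.** Shift = gap in mean FIM change by completeness × imbalance. The gap is not in the documents; I assume 5 to 15 points.

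| Gap | Shift at 30 points | Share of 13 | In SE units |
|---|---|---|---|
| 5 | 1.5 | 12% | 0.3 |
| 10 | 3.0 | 23% | 0.6 |
| 15 | 4.5 | 35% | 0.9 |

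At a typical imbalance of one SD the shift is about 0.8 points (5 × 0.16) to 3.0 points (15 × 0.20).

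**How far could it go?** Moving the estimate by half the planned effect (6.5 points) needs an imbalance of 6.5/15 = 43 points at the widest gap. The probability is 5.0% at K = 15 and 1.1% at K = 10, both directions combined. At a 10-point gap it needs 65 points, with probability about 0.02% to 0.03%. At a 5-point gap it cannot happen (6.5/5 exceeds 1).

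**Precision.** If covariates explain a fraction R² of the variance, the effect size becomes 1.07/√(1 − R²). Exact power at 20:10 rises from 76.0% (R² = 0) to 80.3% (0.1), 84.6% (0.2) and 89.0% (0.3). These keep 28 degrees of freedom, so they are slightly generous, and the R² values are assumptions.

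**The case against.** Much of the case on the other side stands.

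- *Bias.* A reader might infer that the result could not be credited to EAW. The documents do not support that. Leaving a prognostic factor out of the stratification does not bias a randomised comparison, and the t-test keeps an error rate of about 5%. If the preliminary sample mixed complete and incomplete injuries, its SDs of 12 and 13 already contain this variation. The SE of 4.78 then already allows for chance imbalance, and the shift in SE units is part of that SE, not an addition to it.
- *Size.* A reader might also infer that imbalance could create or hide most of the planned difference. The half-effect calculation rules that out as a likely outcome.
- *The link to change.* Section 2.2 says that control may be lost, names neurological level alongside completeness, and describes function, not change from admission to discharge. That completeness affects change in FIM is my inference; no section states it.
- *The population.* Section 5.1 requires eligibility for locomotor training, independent static sitting balance and adequate arm strength. This narrows the range of severity, though it excludes neither motor-complete nor motor-incomplete injury.
- *The stratifier.* It is tempting to call cause the wrong choice. The documents do not show it to be a poor one, and Section 4.1 claims only that it will help with balance. Keeping both factors would make four strata averaging 30/4 = 7.5 people and 10/4 = 2.5 controls, where incomplete blocks could undo the balance sought.

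What these arguments do not answer is the unadjusted analysis. Whatever the stratifier, a severity measure recorded at admission goes unused in the main comparison.

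**Conclusion.** The point holds as one about precision and protection against chance imbalance, not about validity. It is a matter of text that cause is the only stratifier, that the main test is unadjusted, and that completeness is recorded at admission.

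The size rests on two assumed ranges: 20% to 50% of completers with complete injuries, and a 5 to 15 point gap in FIM change. Within them, a 30-point imbalance occurs in about 6% to 25% of trials (10% to 25% except at K = 7 and 8) and moves the estimate by 12% to 35% of the planned effect. That is a moderate effect, worth removing because adjustment costs so little. It does not invalidate the design or show that the allocation scheme must be changed.

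**What to change.** In Section 9.2.1, and in the duplicate text of Section 9.1, replace the unadjusted t-test with a prespecified ANCOVA for each primary outcome. The terms are treatment, the admission score of that outcome, admission AIS in two groups (motor-complete A/B v motor-incomplete C/D) and the stratification factor (traumatic v non-traumatic). State in advance what replaces the Mann-Whitney fallback if the residuals are clearly non-normal, and keep the unadjusted comparison as a supporting analysis.

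The cost is three degrees of freedom: with 30 completers the residual falls from 30 − 2 = 28 to 30 − 5 = 25. No new assessment and no new randomisation list are needed, and the change still works if randomisation has begun.

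Using AIS in place of cause as the single stratifier is an option for the sponsor to consider. It keeps two strata but needs a new list and gives up assured balance on cause.
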